2.2 Intervention models

The planned intervention will be implemented during one school year. The schools in the two intervention arms will provide one extra hour each week to do physical activity. In addition, these schools will also redistribute 5% of the remaining hours of the school week to one extra PE-lesson each week.

The schools randomized to the intervention arms are allocated to one of two models.

The first model is called "**Physical Active Learning**" and consists of the components:

- *Additional physical education*: All activity will be conducted in accordance with the current curriculum. The school's physical education teacher will lead this activity.
- *Physical active learning*: The curriculum of the subjects (i.e. maths, English, Norwegian) will be taught in a physically active manner. The term "Physical active learning" should be stated on the pupils' schedule as 30 minutes per week, preferably not on the same day as the PE-lessons. This activity should be led by the teacher of the current subject.
- *Physical activity*: Without a connection to any specific subject "Physical activity" should be performed 30 minutes a week, preferably on days without PE-lessons and physical active learning. A teacher in collaboration with the pupils should lead the activities, and pupil involvement should be emphasized. The activities should be joyful, and the pupils' well-being should be in focus.

The second model is called "**Don't worry-Be happy**", and is also based on two extra lessons of PA and PE each week. The lessons must have their own names not associated with PE or PA. Examples of such terms are "don't worry" (PE) and "be happy" (PA).

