In this project, it was considered important to be able to detect (or reject) 7% differences in the mean physical activity level between the intervention and control groups. This meant it was necessary to examine 492 pupils in each group. Further, during the trial a drop-out rate of 20% at the individual level should be expected, consequently 590 individuals in each group should be included. However, there should be at least 10 schools per intervention arm (ie per model to be tested) in order for the randomization to have effect. The strategy is then to include schools up to at least 10 schools per intervention arm, and a minimum of 590 individuals will be included in each arm.

Data will be described with suitable measures of central tendency and variability, along with confidence intervals. Mixed models with school as random effect, adjusted for class, individual and baseline values, will be used to investigate the difference in the different variables when comparing the pupils in the two intervention groups with the pupils in the control group. By building up a mixed model, all participants who have data at baseline and everyone who has data at the post- test is included, and thus all data in the project are utilized. Further, per protocol analysis will also be conducted. In these analysis, participants in schools that completed at least 80 % of the intervention program will be compared with the pupils in the control group. A two-sided p-value < 0.05 is considered statistically significant.

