In this phase, the program will continuously be evaluated to assess whether the program work as planned. School leaders and teachers will through logbooks, questionnaires and interviews provide data related to; 1) the extent to which the program and its elements is implemented as planned (fidelity); 2) how much of the program is delivered (dose delivered); 3) how well different program components are delivered (quality); 4) how responsive participants were to the program (responsiveness); and 5) changes made to the program during implementation that enhance its fit with the context (adaptation). Furthermore, parents and pupils will be asked general questions about the school's communication on physical activity and in addition there will be specific questions for participants in the intervention groups about the dosage of the program and the utility value of the various components.

All of these sub-elements will create a common understanding of the premises of the project and thus create a mutual commitment to the implementation of the program. This approach allows a certain degree of local adaptation of the program to ensure implementation, while at the same time there is a need to limit local variation from a research perspective. Good dialogue enables both conditions.

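### Does the 80% completion rule for the per-protocol analysis need a unit, a data source and a date before it can be used?

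*Combined protocol and SAP*

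**What the plan says.** Section 2.5 sets out a mixed model that uses everyone with baseline data and everyone with post-test data. It then adds: "Further, per protocol analysis will also be conducted". The selection rule follows: "participants in schools that completed at least 80 % of the intervention program will be compared with the pupils in the control group". The 80% appears nowhere else in the text available for review, which lacks the front matter and the section between 4.0 and 6.0.

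Section 2.2 describes what a school is asked to deliver:

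- Both intervention arms give one extra hour of activity a week and also "redistribute 5% of the remaining hours of the school week to one extra PE-lesson each week". The length of that lesson in minutes is not stated.
- In the first model the extra hour is split in two. Physically active learning is scheduled as "30 minutes per week, preferably not on the same day as the PE-lessons", and general physical activity "should be performed 30 minutes a week, preferably on days without PE-lessons and physical active learning".
- The second model "is also based on two extra lessons of PA and PE each week".

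Section 4.0, under monitoring and evaluation, says how delivery will be recorded: "School leaders and teachers will through logbooks, questionnaires and interviews provide data related to" five aspects. The first is "the extent to which the program and its elements is implemented as planned (fidelity"), the second is the amount of programme delivered, and quality, responsiveness and adaptation follow. Intervention pupils are also asked about dosage. The section accepts some local adaptation. It does not tie any of these measures to the 80%.

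**The concern.** A threshold without a denominator can be read in several ways. For the first model, 80% could mean total weekly minutes, each of three components, or lessons or weeks held. Several sources could supply the figure, and no one is named to fix the list of schools before follow-up data are seen. With about 10 schools per arm, moving one school in or out changes roughly a tenth of the arm.

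The trial looks for models that schools can use, so some readers may treat the per-protocol figure as what a model achieves when it is delivered. If the school list could be chosen with results in hand, that figure could be steered. The schools are also selected after randomisation, so the comparison does not have the protection that the main analysis has.

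**Working it through.** The plan attaches no calculation to the 80%, so there is no figure to reproduce. The check asks whether the readings classify schools differently, and how much that could move the estimate.

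**1. Do the readings differ?** Take a PE lesson of L minutes (assumed 45 to 60). Weekly total in the first model = L + 30 + 30.

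A school that gives half the active learning and everything else in full delivers (L + 15 + 30)/(L + 60):

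- L = 45: 90/105 = 85.7%.
- L = 60: 105/120 = 87.5%.

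It qualifies on total minutes. On its weakest component it has 50% and does not qualify. So the readings do differ.

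The extreme case: if the other two components are delivered in full, the active-learning minutes needed are 0.8(L + 60) − (L + 30) = 18 − 0.2L, which is 9 of 30 (L = 45) or 6 of 30 (L = 60). The each-component reading needs 24 of 30. The 6 to 9 minutes apply only under full delivery of everything else all year.

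**2. How far apart are the estimates?** Inputs from section 2.5: SD 150 counts/min, inflation factor 1.1, 492 pupils per group, 10 schools per arm, hence 49.2 pupils per school. The numbers of schools kept are assumed.

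- SD of a school mean = 150 × √(1.1/49.2) = 22.4.
- SD of the difference between nested sets of k1 and k2 schools = 22.4 × √(1/k2 − 1/k1). For 8 and 6: 4.6. For 8 and 5: 6.1.
- Against the target of 49: 4.6/49 = 9%; 6.1/49 = 13%.
- Standard error against 10 control schools = 22.4 × √(1/k + 1/10): 10.6 (k = 8), 11.6 (k = 6), 12.3 (k = 5).
- Ratio of the two: 4.6/11.6 = 0.40 to 4.6/10.6 = 0.43 for 8 and 6; 6.1/12.3 = 0.50 to 6.1/10.6 = 0.58 for 8 and 5.

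Baseline adjustment with an assumed correlation r multiplies both quantities by √(1 − r²). For r = 0.5 to 0.7 the SD of the difference becomes 3.3 to 5.3. The ratio does not change, because with equal school sizes it depends only on the numbers of schools.

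**3. Would picking a reading inflate false positives?** I simulated 200,000 trials per setting with no effect, 10 schools per arm and a t-test on school means.

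| What is counted | 8 and 6 schools | 8 and 5 schools |
|---|---|---|
| One reading fixed in advance, p < 0.05 | 5.0% | 5.0% |
| Larger estimate reported with its own two-sided p | 4.9% | 5.1% |
| Either reading significant in favour of the model (nominal 2.5%) | 3.4% | 3.7% |
| Either reading significant in either direction | 6.9% | 7.5% |

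The last row counts significant harm as a success for the selector, so it overstates the risk. The third row is the fair measure of a false claim of benefit. It needs someone to try both readings and report whichever is significant.

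**4. Bias from selecting schools after randomisation.** The factor 1.1 with 49.2 pupils per school implies an intraclass correlation of 0.1/48.2 = 0.0021 and a between-school SD of 150 × √0.0021 = 6.8. The expected standardised mean of the top 5, 7 or 9 of 10 schools is 0.739, 0.456 or 0.170. With an assumed correlation of 0.3 to 0.5 between delivery and activity, the bias runs from 6.8 × 0.170 × 0.3 = 0.3 to 6.8 × 0.739 × 0.5 = 2.5 counts/min.

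**The case for a change.** The best case for a change is that the gap is real and cheap to close. Section 2.5 gives no numerator, denominator, source or date. The section does not call the per-protocol comparison supportive, and its one significance threshold appears to cover it. The two readings do put the same school on different sides of the line. A paragraph and a dated list of schools would settle it.

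The omission stands. The inference drawn from it is weaker:

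- The rule is usable. It refers to the programme as a whole, section 4.0 plans to record how much of it is delivered, logbooks are the first source named there, and section 2.2 gives the weekly content. Nothing in section 2.5 points to an each-component test.
- That the list would be settled after results are known is inferred from silence. The plan does not say when schools are classified.
- The 6-to-9-minute example is possible arithmetically, but it describes a school that is perfect on two components and nearly absent on the third.
- Selection after randomisation is a property of any per-protocol analysis, and defining 80% more closely would not remove it.

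**Conclusion.** No change to the plan follows. The missing unit, source and date are detail that analysts can supply from what the plan already collects, and either reading of 80% is defensible. No rule that the plan states gives a wrong result, and the main mixed model does not depend on the threshold.

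The size supports this. The choice between readings moves the per-protocol estimate by a standard deviation of 4.6 to 6.1 counts/min unadjusted, or 3.3 to 5.3 with baseline adjustment. That is about 0.4 to 0.6 of the estimate's own standard error. Selection bias adds about 0.3 to 2.5 counts/min at the plan's clustering. A determined search over two readings would raise false claims of benefit from 2.5% to 3.4–3.7%.

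These figures rest on the plan's SD, inflation factor and 492 pupils in 10 schools, on an assumed 8 versus 6 or 5 qualifying schools, and on equal school sizes. Stronger clustering than the plan assumes would enlarge the bias, but would leave the ratio to the standard error as it is. The analysts would do well to record their reading of 80% and the qualifying schools before opening the follow-up accelerometer data. That is good practice and does not require an amendment.

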Among adults, the literature shows a strong association between physical activity and the risk of non-communicable diseases,^{5,6} however, this relationship is not as clear among children and adolescents.⁷ This might be due to the fact that these diseases usually manifest in adulthood. At the same time, pathological processes are known to start already in early childhood,⁸ and cross-sectional studies show that physical activity is related to risk factors for non-communicable diseases already at a young age.⁹⁻¹¹ Furthermore, a review has shown that physical activity interventions carried out in the primary school affects some components of physical health.¹² However, it is important to emphasize that this knowledge is inadequate among adolescents in upper secondary school. Early adolescence is characterized by major biological, psychological and social challenges. Results from the "ungdata" report show that the proportion reporting mental disorders in adolescence is high and that the extent of mental disorders increases through adolescence.¹³

The main aim of this study is to investigate whether participation in this project leads to increases in objectively measured physical activity level in 14-year-old boys and girls after a one-year school-based physical activity intervention compared to the control group.

In addition, secondary aims are to investigate whether participation in a one-year school-based physical activity intervention results in changes to the following outcomes when comparing the adolescents in the intervention groups with the adolescents in the control group:

1. Higher objectively measured moderate-to-vigorous physical activity (MVPA)
2. An increase in the proportion adolescents meeting physical activity guidelines (measured objectively)
3. Reductions in time spent sedentary (measured objectively and self-reported).
4. Improvements in muscle strength and cardiorespiratory fitness
5. Improvements in mental health variables including overall psychosocial problems and strengths, quality of life, self-evaluation of competence or adequacy and symptoms of anxiety and depression.
6. Improvements in academic performance in reading and numeracy.
7. Improved learning environment

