2.0 METHODS

School in motion (ScIM) is a school-based cluster-randomized controlled trial (RCT) with three arms. The study last two years, where the first year is used to pilot the models, and the RCT will be completed in the school year 2017-18.

The study is initiated by the Norwegian Directorate for Education and Training.

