2.5 Power calculations and statistical analysis

Power calculations are done to examine how many participants it should be in each group, if a given difference between groups should be significant at a given level (for example, $p < 0.05$) and with a given power (for example, 90% probability of rejecting a false null hypothesis). The required size of the sample depends on how small differences one can detect over time, as well as how large the variation of the current variable is in the population.

In this project, the power calculations are based on the main outcome variable (mean physical activity level [counts/min]). As can be seen in table 1, the number of participants required to detect a specific difference between the groups increases significantly the smaller the difference. Data for SD and mean value of the physical activity variable is based on previous studies conducted in the Norwegian adolescent population.³⁵ The power calculation is performed as a two-sided calculation with an $\alpha = 0.05$ and $1 - \beta = 0.9$. Since this is a cluster sample, the sample size is adjusted for an inflation factor that will be determined by the number of members in the cluster and the intra-class correlation. The correlation is assumed to be small as the cluster is school, therefore the inflation factor is set to 1.1.

Table 1. Power calculations based on the main outcome variable (physical activity expressed as mean counts/min). The column "minimum difference" refers to the level of difference that can be detected between groups.

Variable	Minimum Difference	Variation (SD)	N
Physical activity level (accelerometer)	10 % (70 counts/min)	150 counts/min	246
Physical activity level (accelerometer)	7 % (49 counts/min)	150 counts/min	492
Physical activity level (accelerometer)	5 % (35 counts/min)	150 counts/min	984
Physical activity level (accelerometer)	3 % (21 counts/min)	150 counts/min	2706

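### Do the two model-versus-control comparisons on counts/min, each at two-sided 0.05, need a success rule or a multiplicity adjustment?

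*Combined protocol and SAP*

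**What the plan says.** Section 2.0 describes a "cluster-randomized controlled trial (RCT) with three arms". Section 2.2 adds: "The schools randomized to the intervention arms are allocated to one of two models". The two models differ in content: one includes active teaching of school subjects, the other is built on self-organised activity groups.

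The aims appear at two levels in section 1.0. The opening text gives the project's goal as identifying models, in the plural, that lower secondary schools can use. Later the study aim is put as one question: "The main aim of this study is to investigate whether participation in this project leads to increases in objectively measured physical activity level", compared with control.

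Section 2.5 names mean counts/min as the main outcome and sizes the trial on it. It asks for "at least 10 schools per intervention arm (ie per model to be tested" and plans mixed models "when comparing the pupils in the two intervention groups with the pupils in the control group". The significance criterion is "A two-sided p-value < 0.05 is considered statistically significant". Sections 1.0 to 2.5 contain no success rule across the two models, no joint test, no testing order and no adjustment.

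**The concern.** Two comparisons with a shared control give two chances of a significant result. The study aim, read alone, is one question about the project as a whole. If a positive result for either model answered it, the error attached to that answer would be larger than the printed level. With no rule written down, the choice between either model, both models and the pooled arms could also be made after the results are known. Under no effect of either model, the chance of a false claim of an increase would then range from about 0.5% (both needed) through 2.5% (pooled) to about 4.5% (either). Because the project is meant to supply models for school use, a false positive for one model could matter for policy.

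**Working it through.** **Inputs.** Two-sided 0.05, so 2.5% in the direction of an increase (section 2.5). Three arms (section 2.0). No allocation ratio is stated. The same minimum of 590 pupils per arm suggests about 1:1:1, which I assume and then vary. For power: difference 49 counts/min, SD 150, inflation factor 1.1, 492 per group, design power 90% (section 2.5).

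**The plan's own figure.** The documents give no familywise error rate to reproduce. The sample size can be tried: 2 × (150 × (1.960 + 1.282) / 49)² = 196.9, so 197 per group, and 196.9 × 1.1 = 216.6, so 217. The stated 492 per group does not follow from these inputs. It is nearer the two-group total of 434, but does not match that either. The error rates below do not depend on it; the cost of an adjustment does.

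**Correlation of the two comparisons.** With model arms of size n and a control arm of size m, it is (1/m) / (1/n + 1/m) = n / (n + m). Equal arms give 0.5, a control arm half the size gives 0.667, and one twice the size gives 0.333.

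**Error if neither model works and either one counts.** With equal arms, P(both Z > 1.96) = 0.0046 from the bivariate normal distribution, so P(at least one Z > 1.96) = 0.025 + 0.025 − 0.0046 = 0.0454. In either direction the probability is 0.0907.

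| Control size relative to a model arm | False claim of an increase | Any false difference |
|---|---|---|
| half | 4.2% | 8.5% |
| equal | 4.5% | 9.1% |
| twice | 4.7% | 9.5% |

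A school-level simulation with 10 schools in each of three arms (27 df) gives 4.5% and 9.0%. The 10 control schools are an assumption, since the plan sets that minimum only for the intervention arms.

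**Error under the other readings.**
- Each model claimed on its own: 2.5% for an increase and 5% two-sided, per model.
- The two model arms pooled against control: one test, 2.5% and 5%.
- Both models must succeed: 0.5% if neither works, and at most 2.5% if one does.

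Only the either-model rule for a single aim raises the error above the printed level.

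**Cost of an adjustment.** Taking 492 per group at face value, the noncentrality is 49 / (150 × √(2 × 1.1 / 492)) = 4.885 and power per comparison is 99.8%. An adjustment then costs next to nothing. But that power conflicts with the stated 90% design. If 492 were a two-group total (246 per arm), the noncentrality would be 3.454 and power 93%. With 492 per group, true power of 90% or 80% corresponds to inflation factors of about 2.5 or 3.3. Simulated power at those two levels, with equal arms:

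| Power (%) | Unadjusted | Closed test | Step-down Dunnett |
|---|---|---|---|
| 90% case: per comparison, both models work | 90.0 | 87.9 | 88.5 |
| 90% case: at least one claim, both work | 96.8 | 92.8 | 94.1 |
| 90% case: the one model that works | 90.0 | 87.9 | 85.0 |
| 80% case: per comparison, both models work | 80.0 | 75.7 | 76.9 |
| 80% case: at least one claim, both work | 91.3 | 83.4 | 86.0 |
| 80% case: the one model that works | 80.0 | 75.7 | 72.4 |

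The closed test therefore loses 2.1 to 4.3 points per comparison, and 4.0 to 7.9 points for at least one claim.

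**The case for a change.** The best argument for a change is that the study aim in section 1.0 is written as one question about taking part in the project, while the analysis offers two routes to a positive answer. One sentence would settle which route counts, it needs no extra pupils or schools, and it would close off a choice made after the data are seen. The arithmetic behind the argument is sound.

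What stands is that the plan is silent on how the two results combine. What does not stand is the step from silence to inflated error. Nothing in the plan says that one model's success settles the aim for both. The project goal in section 1.0 and the wording on schools per model in section 2.5 favour separate answers, and under that reading the plan is sound as written. Section 2.5 also states its 7% target as a difference between intervention and control, which leaves a pooled comparison possible, and that would carry no inflation. The concern about choosing a rule afterwards is limited too: the main outcome is named, there are only two models, and the planned comparison covers both, so a reader of the results can see one success beside one failure.

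**Conclusion.** No change is needed. The gap is one of detail that analysts would fill sensibly by estimating each model against control on counts/min, reporting both with confidence intervals, and making any claim for the model concerned. Under that practice the error is 2.5% per model for an increase (5% two-sided), as the plan states. The figures of 4.5% and 9.1% rest on three assumptions together: neither model works, the arms are about equal, and a win on either model is taken to prove one project-level aim. The third is not in the plan.

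Whether two distinct programmes sharing a control should be adjusted as a family is a trade-off on which reasonable statisticians disagree. If true power is 80 to 90%, the closed test would give up about 2 to 4 points per comparison and 4 to 8 points for at least one claim. The near-zero cost seen at 99.8% power relies on a group size that the plan's own inputs do not produce. The conclusion would differ only if the report used one model's success to claim an effect of the project as a whole.

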1.0 INTRODUCTION

As part of creating a better knowledge base for future work on physical activity among adolescents, the "Folkehelsemeldingen - Mestring og muligheter" has defined a trial with a selection of secondary schools where students will receive about four hours of physical activity and physical education during the week.¹ The experiment should be organized so as to best study the effects of increased physical activity (PA) and/or physical education (PE) on the participants physical and mental health, learning and learning environment and, if possible, how it affects the development of PE as a subject.

The main aim of this project is thus defined to find models of PA/PE that can be used in Norwegian lower secondary schools. These models are intended to have an impact on the adolescents' physical health, mental health, learning and learning environment. The fact that the intervention models should affect four different outcomes will make this project very challenging. However, as we face a global trend with increased prevalence and premature deaths caused by non-communicable diseases such as cardiovascular disease, type 2 diabetes, chronic lung disease and cancer this project is timely. Worldwide, these diseases cause two thirds of all deaths and one of four deaths among those below 60 years of age.

Non-communicable diseases are partly due to increased sedentary lifestyle,² and physical inactivity is defined as a significant public health problem for people of all ages.³ Globally, physical inactivity is referred to as one of the four leading causes of mortality.² According to the World health organization, 10% of all deaths in Europe are related to inactivity.⁴ In May 2012, the World Health Assembly (WHA) adopted the target of reducing premature death of non-communicable diseases by 25% by 2025. WHO has identified four overall indicators and targets to reach this target. One of the goals is that the proportion that is physically inactive should be reduced by ten percent.

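### The two-sided p < 0.05 rule covers every secondary outcome for both models, with no order, adjustment or exploratory label among them, so a false claim of some improvement is likely

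*Combined protocol and SAP*

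**What the plan says.** Sections 2.3 and 2.5 make accelerometer-measured physical activity, as mean counts/min, the main outcome, and the sample size rests on it alone. Section 1.0 separates this main aim from seven secondary aims, introduced by "In addition, secondary aims are to investigate whether participation in a one-year school-based physical activity intervention results in changes to the following outcomes". Several aims are worded as a direction of benefit. Aim 5, for example, reads "Improvements in mental health variables including overall psychosocial problems and strengths, quality of life, self-evaluation of competence or adequacy and symptoms of anxiety and depression".

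For analysis, section 2.5 says mixed models "will be used to investigate the difference in the different variables", "comparing the pupils in the two intervention groups with the pupils in the control group". The paragraph ends with a single criterion: "A two-sided p-value < 0.05 is considered statistically significant". Nothing limits that criterion to counts/min. The text available for review, in which section 2.5 appears in full, contains no testing order among the secondary outcomes, no division of alpha, no multiplicity adjustment and no statement that secondary results are exploratory. It also does not say whether the questionnaires are analysed as totals or by subscale.

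**The concern.** Leaving secondary outcomes unadjusted is common and does little harm when they only support the primary result. Here they carry more weight. Section 1.0 says the models are intended to affect physical health, mental health, learning and learning environment, and remarks that "The fact that the intervention models should affect four different outcomes will make this project very challenging". Counts/min speaks only to the first of these four areas. Any statement about the other three must come from aims 5 to 7, where every test would be declared significant or not at the same unadjusted level.

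The project is meant to identify models for use in Norwegian lower secondary schools. If the plan is followed as written, a model with no effect on any secondary outcome would still have a substantial chance of being reported as having significantly improved at least one of them.

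**Working it through.** **Plan's own figure.** The documents give no error rate across outcomes. The only stated figure is the per-test level: two-sided 0.05, that is 0.05/2 = 0.025 in the direction of improvement.

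**Counting the outcomes** (aims from section 1.0, instruments from section 2.3):

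| Aim | One score per instrument | By subscale or topic |
|---|---|---|
| 1 MVPA | 1 | 1 |
| 2 Meeting activity guidelines | 1 | 1 |
| 3 Sedentary time (objective, self-reported) | 2 | 2 |
| 4 Running test, sit-ups, handgrip, long jump | 4 | 4 |
| 5 SDQ, HSCL-10, KIDSCREEN-27, SPPA | 4 | 5 + 1 + 5 + 7 = 18 |
| 6 Reading, numeracy | 2 | 2 |
| 7 Classroom Climate Scale | 1 | 4 |
| Total | 15 | 32 |
| Tests (x 2 models) | 30 | 64 |

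Aim 5 alone is 4 x 2 = 8 tests or 18 x 2 = 36 tests. The count leaves out the per-protocol repeats, the Pupil Survey, self-reported marks and the other intensity categories.

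**Assumptions, none of them given in the documents.** There is no true effect on any secondary outcome. Each test holds its nominal level. Each model is compared separately with one shared control arm of equal size, so the two contrasts on one outcome correlate at 0.5. All outcomes share a common correlation r.

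**Expected number of false improvements**, whatever r is: 30 x 0.025 = 0.75, and 64 x 0.025 = 1.6.

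**Uncorrelated outcomes (r = 0), by formula.** For one outcome, the chance that both contrasts exceed 1.96 is about 0.0046 (bivariate normal, correlation 0.5). The chance that at least one does is 2 x 0.025 - 0.0046 = 0.0454. For k outcomes the chance of at least one false improvement is 1 - (1 - 0.0454)^k:
- k = 4: 17%
- k = 15: 50%
- k = 18: 57%
- k = 32: 77%

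**Correlated outcomes, by simulation** of null trials, counting any z > 1.96 (false improvement) and any |z| > 1.96 (either direction):

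| Tests | False improvement, r = 0.5 | Range, r = 0.8 to 0 | Either direction, r = 0.5 |
|---|---|---|---|
| 30 (all aims, one score per instrument) | 29% | 17-50% | 56% |
| 64 (all aims, by subscale) | 41% | 22-77% | 75% |
| 8 (aim 5, one score per instrument) | 14% | 10-17% | 27% |
| 36 (aim 5, by subscale) | 32% | 18-57% | 61% |

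A common r across domains is a simplification. With r = 0.5 within domains and 0.2 between them, the false-improvement chance is 38% for 30 tests and 52% for 64, so the simplification does not exaggerate the result in that case.

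**Against the nominal rate.** On the narrow count, the most favourable correlation examined gives 17%, and 17/2.5 = 6.8, about seven times the nominal rate.

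**The case against.** The strongest reply is that the plan already has a hierarchy: one main outcome, with everything else labelled secondary and introduced as a matter to investigate. The plan claims no family-wise control, and each test keeps its ordinary 5% rate. That much is true. A reader might infer that the plan has no hierarchy at all, and the documents do not support that; what is missing is any structure among the secondary outcomes. The secondary label also does not settle the matter, because the significance criterion is not limited to the main outcome and section 1.0 looks for effects in domains that only secondary outcomes cover.

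A second reply is that the larger counts depend on scoring the plan never states. This stands. Section 2.3 describes what the questionnaires contain, not what will be tested, and aim 5 speaks of overall psychosocial problems, which points towards a total score. The 36 and 64 tests are therefore assumptions. The narrow count does not need them.

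Third, the figures depend on a correlation the documents do not give. This also stands, and is why ranges are shown; 29% or 41% should not be read as a fixed property of the plan.

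Two further inferences are tempting. One is that a single significant mental-health score would count as an improvement in mental health. Section 2.5 sets significance variable by variable and contains no such domain rule. The other is that mental health is the domain most likely to show a false finding. That follows only from the subscale count; with one score per instrument, mental health has four outcomes, the same as fitness and strength.

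**Conclusion.** The concern holds in a limited form. The inference on counts/min is not in question here. Among the secondary outcomes, one unadjusted rule applies throughout, and the chance of at least one false significant improvement is about 29% over 30 tests at an assumed correlation of 0.5. Scoring by subscale would raise it to about 41%. Both figures assume no true secondary effect and two separate model-versus-control contrasts. The exact size depends on the unknown correlation and on scoring choices the plan leaves open. The conclusion does not: even the most favourable correlation examined leaves the rate on the narrow count far above nominal. This should be corrected because it bears on what the trial can claim in three of its four target areas.

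**What to change.** In section 2.5, confine the statistical-significance criterion to counts/min. State that aims 1-7 and their subscales are secondary or exploratory and will be reported as model-versus-control estimates with 95% confidence intervals, without confirmatory claims.

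If the sponsor wants a claim in a particular domain, name one lead variable for it in advance (for aim 5, for example, one overall mental-health score) and apply Holm across the lead variables and both models. The remaining scores stay descriptive.

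The change takes a few sentences and needs no new data. It has a price: isolated secondary results just under 0.05 can no longer be called significant. The Holm option also lowers power for lead variables the trial was not sized for, since section 2.5 sizes counts/min only.
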